# 4.1.3.2 Other Secondary Endpoints .

All of the following endpoints will be analyzed using the same methodology as the primary endpoint:

- The change from Baseline in knee pain as measured by daily VAS Pain Score and average weekly VAS Pain Score (100 mm VAS) through 26 weeks post treatment comparing the Cingal® arm to the TH arm and Placebo arm, the Cingal arm to the Placebo arm, and the TH arm to the Placebo arm.
- The change from Baseline in knee pain as measured by daily NRS Pain Score and average weekly NRS Pain Score (0-10 NRS) through 26 weeks post treatment comparing the Cingal® arm to the TH arm and Placebo arm, the Cingal arm to the Placebo arm, and the TH arm to the Placebo arm.
- The change from Baseline in WOMAC Physical Function score at 26 weeks post treatment comparing the Cingal® arm to the TH arm and Placebo arm, the Cingal arm to the Placebo arm, and the TH arm to the Placebo arm.
- The change from Baseline in WOMAC Stiffness score at 26 weeks post treatment comparing the Cingal® arm to the TH arm and Placebo arm, the Cingal arm to the Placebo arm, and the TH arm to the Placebo arm, the Cingal arm to the Placebo arm, and the TH arm to the Placebo arm.
- The change from Baseline in Total WOMAC score at 26 weeks post treatment comparing the Cingal® arm to the TH arm and Placebo arm, the Cingal arm to the Placebo arm, and the TH arm to the Placebo arm.
- The change from Baseline in the Patient Global Assessment at 26 weeks post treatment in the Cingal® arm compared to the TH arm and Placebo arm, the Cingal arm to the Placebo arm, and the TH arm to the Placebo arm.

That is, Data will be analyzed via an analysis of variance (ANOVA) with a term for treatment and baseline pain score as a covariate. The primary hypothesis(es) will be tested by a predefined contrast for comparing the Cingal Arm to the triamcinolone hexacetonide (TH) Arm, the Cingal Arm to the Placebo Arm, and the TH Arm to the Placebo Arm. Formally, the hypotheses to be tested is:

```
H_0: \mu_{DC} = \mu_{DT} versus H_A: \mu_{DC} \neq \mu_{DT}. (Primary Cingal to TH) H_0: \mu_{DC} = \mu_{DP} versus H_A: \mu_{DC} \neq \mu_{DP}. (Primary Cingal to Placebo) H_0: \mu_{DT} = \mu_{DP} versus H_A: \mu_{DT} \neq \mu_{DP}. (Primary TH to Placebo)
```

Where  $\mu_{DC}$  is the mean change from baseline in the Endpoint Score for the Cingal Arm at 26 weeks,  $\mu_{DT}$  is the mean change from baseline in the Endpoint Score for the triamcinolone hexacetonide Arm at 26 weeks, and  $\mu_{DP}$  is the mean change from baseline in the Endpoint Score

for the Placebo Arm at 26 weeks. Since there are three treatment groups in this study, this hypothesis will be tested using a one way ANOVA and constructing a contrast for this hypothesis. This process is the same as using a baseline Endpoint Score adjusted two-sample t-test with the common variance estimate from the ANOVA.

The anticipated SAS code for this analysis is given as:

The mean difference will be estimated and tested using the contrasts from PROC GLM on the responses at the 26 week time period.

```
PROC GLM DATA=EFF;
WHERE VISITNO = 26;
CLASS TRT;
MODEL PARMDIFF = BASEPARM TRT / TYPE3 ALPHA=0.05;
ESTIMATE 'CINGAL VS PLACEBO' TRT 1 -1 0;
ESTIMATE 'CINGAL VS TH' TRT 1 0 -1;
ESTIMATE 'PLACEBO VS TH' TRT 0 1 -1;
LSMEANS TRT / DIFF CL ALPHA=0.05;
FORMAT TRT TRTF.;
RUN;
```

In this model, the PARMDIFF is the difference in Endpoint Score from baseline. The variable TRT is a categorical variable where 1 = Cingal, 2=Placebo, and 3=TH. The variable BASEPARM is the baseline Endpoint Score and the variable VISITNO is the visit number identifier. ODS statements will be used to output the contrasts and the mean differences into data sets that can be easily displayed using PROC REPORT. The primary analysis will be comparing Cingal to TH.

The tables for this analysis will be displayed as:

Summary of Least Squares Means at 26 weeks – Endpoint Score

Treatment Group	Mean Percent Improvement LS Mean	Standard Error
Cingal		
Placebo		
TH		

Summary of Differences in Mean Responses at 26 Weeks – Endpoint Score

Treatment Group	Mean Percent Improvement	Standard Error	Lower Confidence Limit	Upper Confidence Limit	p-value
Cingal – Placebo					
Cingal – TH (Primary)					
Placebo - TH					

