11 STATISTICAL CONSIDERATIONS

The statistical analysis of the study is described in detail in a separate version-controlled prospective Statistical Analysis Plan (SAP). However, the statistical methodology described in this section of the protocol will be the basis for the detailed SAP. It should be noted that this is a pilot study designed to assess the differences between Cingal and TH for change in pain and function scores between Baseline and 26 weeks post treatment. This change in scores will be conducted on multiple assessments and therefore, no formal hypothesis testing will be performed.

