11.2 Primary Efficacy Endpoint

The primary efficacy endpoint is the change from Baseline in knee pain as measured by the WOMAC Pain Score (100 mm VAS).

The time point of main interest is 26 weeks, but in order to study the time course profile, the data will be analyzed at each time point. Data will be analyzed via an Analysis of Variance (ANOVA) with a term for treatment and Baseline pain score as a covariate. The primary analysis will be conducted by constructing 95% confidence intervals using the predefined contrasts for comparing the Cingal® arm to the TH arm, the Cingal arm to the Placebo arm, and the TH arm to the Placebo arm. These confidence intervals will be constructed as:

$$(\overline{X}_{\iota} - \overline{X}_{J}) \pm z_{\alpha/2} s_{D}$$

Where $\overline{X_i}$ and $\overline{X_j}$ are the Least Squares Means for the two treatments being utilized and s_D is the standard deviation of that difference.

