11.3.1 OMERACT-OARSI responder

The OMERACT-OARSI response rates for the Cingal® arm, TH arm, and the Placebo arm will be calculated for each time point and all pairwise difference confidence intervals will be constructed utilizing the normal approximation to the binomial distribution [29, 30].

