11.3.2 VAS Knee Pain (0-100mm VAS)

The time point of main interest is 26 weeks, but in order to study the time course profile, the data will be analyzed at each time point. The average weekly pain score and the Area Under the weekly pain Curve (AUC) will be analyzed via an ANOVA and a mixed effects repeated measures ANOVA with a term for treatment and Baseline pain score as a covariate. The analysis will be conducted by constructing 95% confidence intervals using the predefined contrasts for comparing the Cingal® arm to the TH arm, the Cingal arm to the Placebo arm, and the TH arm to the Placebo arm.

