11.3.3 NRS Knee Pain (0-10 NRS)

The time point of main interest is 26 weeks, but in order to study the time course profile, the data will be analyzed at each time point. The average weekly pain score and the Area Under the weekly pain Curve (AUC) will be analyzed via an ANOVA and a mixed effects repeated measures ANOVA with a term for treatment and Baseline pain score as a covariate. The analysis will be conducted by constructing 95% confidence intervals using the predefined contrasts for comparing the Cingal® arm to the TH arm, the Cingal arm to the Placebo arm, and the TH arm to the Placebo arm.

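### The SAP departs from protocol section 11 without saying so: the diary AUC and repeated-measures analyses are gone, analysis at each time point becomes optional, and the Evaluator Global, rescue-use and treatment-failure plans no longer match.

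*SAP*

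**What the plan says.** Protocol section 11 states that "the statistical methodology described in this section of the protocol will be the basis for the detailed SAP". SAP 4.1 describes itself as supplying the detail of the analysis set out in the protocol. It lists no departures.

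For diary VAS pain, protocol 11.3.2 gives one visit priority but keeps the others, in these words: "main interest is 26 weeks, but in order to study the time course profile, the data will be analyzed at each time point". For diary NRS pain, protocol 11.3.3 adds that the weekly average and the "Area Under the weekly pain Curve (AUC) will be analyzed via an ANOVA and a mixed effects repeated measures ANOVA"; 11.3.2 has the same provision for VAS. The primary endpoint (11.2) carries the same commitment: "in order to study the time course profile, the data will be analyzed at each time point". OMERACT-OARSI response rates (11.3.1) "will be calculated for each time point and all pairwise difference confidence intervals will be constructed utilizing the normal approximation to the binomial distribution".

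SAP 4.1.3.2 lists the two diary endpoints, still defined over the whole 26 weeks, together with the WOMAC function, stiffness and total scores and the Patient Global Assessment. It says: "All of the following endpoints will be analyzed using the same methodology as the primary endpoint". The method that follows is confined to one visit: "The mean difference will be estimated and tested using the contrasts from PROC GLM on the responses at the 26 week time period". Its hypotheses and table titles also refer to week 26.

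SAP 4.1.3.9 analyses rescue medication as the proportion of users by Fisher's exact test. SAP 4.1.4 makes comparisons at other time points optional, keeps pill use between visits as a descriptive comparison, and counts treatment failures up to week 12.

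**The concern.** The stated objective covers both the size and the duration of the steroid's contribution to pain relief. A single estimate at week 26 speaks to size at that visit. The time-course, AUC and repeated-measures analyses are the ones that speak to duration, and those lose their place in the SAP.

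If the SAP is followed as written, its own diary endpoints, defined through 26 weeks, are not estimated over that period. Optional wording also leaves the choice of time points to be made after results are known. Two further secondary endpoints are affected. The Evaluator Global Assessment has no secondary analysis, and rescue use is reduced to a yes/no outcome without interval estimates. The failure count would cover less than half of the period that the protocol defines.

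**Working it through.** No figure in the plan is disputed, so the check is mainly a side-by-side reading. The design figures were confirmed first, to show that they are untouched. With 99 per arm, SD 20 and two-sided 5%, power = Φ(δ / (20·√(2/99)) − 1.96). For δ = 8 this is Φ(2.81 − 1.96) = 80.4%; for δ = 10 it is Φ(3.52 − 1.96) = 94.0%. Both agree with protocol 11.1 (80% and over 90%).

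| Item | Protocol | SAP |
|---|---|---|
| Diary VAS and NRS (secondary) | 11.3.2, 11.3.3: each time point; weekly average and AUC; ANOVA and mixed repeated-measures ANOVA | 4.1.3.2: primary-endpoint model at week 26; AUC appears nowhere; repeated measures only under missing data (4.5) |
| WOMAC pain, function, stiffness, total; Patient Global | 11.2, 11.3.4 to 11.3.7: each time point, week 26 of main interest | 4.1.2, 4.1.3.2: week 26; other times optional (4.1.4) |
| Evaluator Global | 11.3.8: each time point | Secondary in 3.2; absent from the 4.1.3.2 list; exploratory item only |
| OMERACT-OARSI | 11.3.1: each time point, pairwise confidence intervals | 4.1.3.1: week 26, Fisher p-values; other times optional (4.1.4) |
| Rescue medication | 11.3.9: baseline-adjusted ANOVA, 95% confidence intervals, each time point | 4.1.3.9: percentage of users, Fisher's test, p-values only; pill use descriptive in 4.1.4 |
| Treatment failure (exploratory) | 2 and 11.4: to the week-26 visit | 4.1.4: to the week-12 visit |

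Counts that follow:

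- **Endpoints with a commitment to each time point.** Protocol: 1 primary (11.2) + 9 secondary (11.3.1 to 11.3.9) = 10. SAP 4.1.2 and 4.1.3: 0.
- **Committed interval estimates, visit-based continuous endpoints.** Protocol: 6 endpoints × 6 visits (weeks 1, 3, 6, 12, 18, 26) × 3 contrasts = 108. SAP: 5 endpoints (Evaluator Global not listed) × 1 visit × 3 contrasts = 15. The difference is output that is no longer promised; SAP 4.1.4 would still allow it.
- **Diary scales without AUC or a repeated-measures model in the SAP:** 2 of 2.
- **Treatment failure.** 26 − 12 = 14 weeks left out, 14/26 = 54% of the period; the visits at weeks 18 and 26 are 2 of 6 follow-up visits.

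**The case against.** The strongest reply is that little is truly lost. SAP 4.1.4 allows comparisons at any time from baseline to week 26, names the WOMAC scores, OMERACT-OARSI and both global assessments, and gives methods (ANOVA with contrasts, Fisher's test). SAP 3.3 also lists the diary scores as exploratory. That is correct: a reader might infer that the time-course analyses are abolished, and the documents do not support this. What has gone is the commitment. For the diary scores, the methods list in 4.1.4 does not name them, and no AUC or repeated-measures model is given anywhere.

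SAP 4.5 does say that a mixed repeated-measures analysis will be used. It says so in the argument about missing data and gives no diary model, so it does not replace protocol 11.3.2 and 11.3.3.

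On rescue use, a reader might infer that the amount taken disappears from the SAP. It does not: both protocol 11.4 and SAP 4.1.4 name pill use between visits, compared descriptively. What changes is the secondary analysis. Two further inferences also fail. The rescue baseline need not fall in the 48-hour washout, because a pill count at the Baseline visit covers the screening period. Nor does the 26-week label on the rescue table imply use on the visit day alone, since other SAP tables carry the same label and the section heading covers the whole 26 weeks.

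The missing Evaluator Global entry and the week-12 window may be clerical. SAP numbering jumps from 4.1.3.2 to 4.1.3.9, which fits merged subsections and a lost item. That explains the errors but does not remove them. Finally, this is a pilot study, which limits the consequences.

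**Conclusion.** The point holds as an undeclared mismatch between the two documents, and it should be corrected. The diary analyses matter most: the SAP keeps the 26-week diary endpoints but gives them a week-26 model, for 2 of 2 scales. Commitment to each time point falls from 10 of 10 primary and secondary endpoints to none. The Evaluator Global Assessment is left as exploratory only, rescue use loses its adjusted interval estimates, and the failure window loses 14 of 26 weeks.

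This rests on the current text alone and needs no assumption about data. It does not extend to the main result: the week-26 WOMAC pain estimate and the sample size stand. The number of treatment failures that would be missed cannot be stated, because the documents give no failure rate.

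**What to change.** Amend the SAP before unblinding:

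- **4.1.3.2, diary scores:** restore the protocol's weekly-average, AUC and repeated-measures analyses for VAS and NRS.
- **4.1.2 to 4.1.3:** commit to estimates at each time point for the primary and secondary endpoints, with week 26 as the main one.
- **4.1.3.2, list:** add the Evaluator Global Assessment.
- **4.1.3.9:** reconcile with protocol 11.3.9 by analysing pill use between visits, the measure that both documents already name, with confidence intervals. Protocol 11.3.9 does not define its baseline, so state it; screening-period use from the Baseline pill count or the diary is one option. Keep the percentage of users as descriptive, with one stated window.
- **4.1.4:** reconcile the treatment-failure window with the definition in protocol sections 2 and 11.4.

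If any of these departures is intended, list and justify it in the SAP instead.

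The cost is SAP wording and a few more tables. Daily diary pain, diary rescue use, pill counts and all visit assessments are already collected, so visits and sample size do not change.

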# 4.1.3.9 The usage of rescue medication through 26 weeks post treatment comparing the Cingal group to the triamcinolone hexacetonide group.

The percentage of subjects using rescue medications will be calculated and tested using Fisher's exact test. Formally, the hypothesis to be tested is:

```
H0: \pi_C = \pi_T versus H0: \pi_C \neq \pi_T
H0: \pi_C = \pi_P versus H0: \pi_C \neq \pi_P
H0: \pi_T = \pi_P versus H0: \pi_T \neq \pi_P
```

Where  $\pi_C$  is the usage rate for the Cingal Arm,  $\pi_T$  is the usage rate for the triamcinolone hexacetonide Arm, and  $\pi_P$  is the usage rate for the Placebo Arm.

This will be estimated and tested using PROC FREQ with the EXACT option. The results will be displayed similar to:

Summary of the Usage Rates at 26 Weeks

Parameter	Cingal	Placebo	ТН
Estimate n/N (%)			
Cingal vs TH (Primary) (p-value)			
Cingal vs Placebo (p-value)			
Placebo vs TH (p-value)			

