2 DEFINITIONS

Baseline: The assessments performed prior to the study injection after the Screening Visit.

Blinded Evaluator: The Blinded Evaluator will be a physician, research nurse, registered physiotherapist or physician assistant trained by the Principal Investigator (PI) to perform the assessments outlined in the protocol. The Blinded Evaluator will complete the Physical Exam, Physical Evaluation of both knees, Range of Motion (ROM) assessment of both knees, and the Evaluator Global Assessment.

End of Study: End of study is defined as the last subject's last visit.

Enrolled: A Subject who has signed the informed consent form (ICF) is enrolled.

Index Knee: The knee that meets the eligibility criteria for treatment. The Index knee may also be termed the "study knee". In subjects with bilateral knee Osteoarthritis (OA), where both knees meet eligibility criteria, the more symptomatic knee is the Index knee.

Institutional Review Board (IRB) refers to an independent body (e.g. Research Ethics Boards, Independent Ethics Committees) whose responsibility is to ensure the protection of rights, safety and well-being of human subjects involved in a trial. Committees with these responsibilities will be referred to in this document as IRB.

Rescue Medication: Acetaminophen will be distributed as the rescue medication. It is the only medication that should be taken for knee pain during the entire study. Rescue medication will be discontinued at least 48 hours prior to Baseline and all follow-up visits.

Treating Physician: The Treating Physician will most often be the PI. He/she will administer the Cingal[®], Triamcinolone Hexacetonide (TH), or Placebo injection but will not participate in the efficacy evaluation.

Treatment Failure: A Subject who undergoes a procedure or uses a medication (other than the rescue medication) for the treatment of OA in the Index knee at any time after the study injection through the 26-week visit.

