11.3 Secondary Efficacy Endpoints

There are many secondary endpoints to be investigated in this study. Again, these endpoints will be evaluated utilizing pairwise confidence intervals. For continuous variables the confidence intervals will be constructed as in section 11.2. For the dichotomous variables, the confidence intervals for the responder rates will be constructed utilizing the normal approximation to the binomial.

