11.3.9 Rescue Medication Usage

The time point of main interest is 26 weeks, but in order to study the time course profile, the data will be analyzed at each time point. Data will be analyzed via an ANOVA with a term for treatment and Baseline score as a covariate. The primary analysis will be conducted by constructing 95% confidence intervals using the predefined contrasts for comparing the Cingal® arm to the TH arm, the Cingal arm to the Placebo arm, and the TH arm to the Placebo arm.

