#### 4.2 STATISTICAL METHODS

Tabulation of summary statistics, graphical presentations, and statistical analyses will be performed using SAS® software 9.4 or higher version. Where not otherwise specified, the last pretreatment observation will be used as baseline for calculating post-treatment changes from baseline. The primary presentations and analyses will be based on data pooled across study centers. Relevant summaries for individual centers, or combinations of centers, may be presented for primary data. All testing and confidence intervals will use a significance level of 5%.

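### SAP 4.1.3.9 replaces the protocol's baseline-adjusted analysis of rescue usage with a Fisher test of percent users, and so loses sensitivity to a reduction in amount

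*SAP*

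**What the plan says.** Protocol 11.3.9 (Rescue Medication Usage): "Data will be analyzed via an ANOVA with a term for treatment and Baseline score as a covariate". It asks for 95% confidence intervals for the three pairwise contrasts, with 26 weeks of main interest and every time point analysed. Protocol 11.3 says of the secondary endpoints in general that "these endpoints will be evaluated utilizing pairwise confidence intervals", and this includes the dichotomous ones. Protocol section 11 states that its methodology is to be the basis for the SAP.

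SAP 4.1.3.9: "The percentage of subjects using rescue medications will be calculated and tested using Fisher's exact test". No threshold for being a user is given, so any use is the natural reading. There is no baseline term and no other time point, and the table has rows for n/N (%) and p-values only. The heading reads "The usage of rescue medication through 26 weeks post treatment", while the table is titled "Summary of the Usage Rates at 26 Weeks".

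The number of pills taken between visits appears in SAP 4.1.4 and in protocol 11.4, in both places as an exploratory item to be compared descriptively.

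**The concern.** A baseline-adjusted ANOVA implies a quantitative measure, although protocol 11.3.9 names no unit. The SAP turns it into a yes/no measure. A subject who goes from daily tablets to a single tablet in 26 weeks counts exactly as before; only a subject who avoids rescue altogether changes category. Over a window that long, most subjects in every arm may be users, and the arms can then differ clearly in amount while the percentages stay close together. A p-value without an interval also hides how uncertain a null result would be. At stake is whether this endpoint can show that Cingal subjects needed less acetaminophen than TH subjects. The protocol describes pill use as an indirect measure of pain.

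**Working it through.** **1. The texts side by side.**

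| | Protocol 11.3.9 (with 11.3) | SAP 4.1.3.9 |
|---|---|---|
| Measure | quantitative (implied, no unit) | percent of subjects using rescue |
| Method | ANOVA, treatment and baseline | Fisher's exact test |
| Baseline use | covariate | not used |
| Result shown | pairwise 95% CI | p-value |
| Time points | 26 weeks and each other one | 26 weeks only |

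The SAP gives no reason for the change.

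**2. The plan's own power figure.** There is none for rescue. The only one is for WOMAC pain (SAP 4.1.1): 99 per arm, SD 20, difference 8, 80% power. Check: 8 / (20 × √(2/99)) = 8 / 2.843 = 2.814; 2.814 − 1.960 = 0.854; Φ(0.854) = 80.4% (80.0% with the noncentral t). It reproduces, so 99 per arm and two-sided 5% are used below.

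**3. A simple model (assumed rates).** Let total pills be negative binomial with mean μ and shape k. Then P(any use) = 1 − (k/(k+μ))^k. Take k = 1, μ = 20 for TH and 0.6 × 20 = 12 for Cingal.
- TH: 1 − 1/21 = 95.2%
- Cingal: 1 − 1/13 = 92.3%
- Exact Fisher power: 8%
- Unadjusted t-test on pills: 93%

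Over k = 0.5 to 2 and TH means of 5 to 120 pills, a 40% lower mean gives Fisher power of 0% to 32% and t-test power of 64% to 100%.

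**4. A fuller model (assumed rates).** TH subjects use rescue on 5% of days on average. Subject rates are gamma with CV 1 and constant over follow-up. Baseline use is 1.3 times higher, with correlation 0.6. There are 12 baseline and 168 follow-up days, with washout removed, and 1 + Poisson(2) pills per use-day.

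Hand check of the user rates: with CV 1, P(no use) ≈ 1/(1 + mean use-days).
- TH: 168 × 0.05 = 8.4 days, 1/9.4 = 10.6%, so 89.4% users
- Cingal, 40% lower: 8.4 × 0.6 = 5.04 days, 1/6.04 = 16.6%, so 83.4% users

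Simulation gives 89.4% and 83.7%. The power of each analysis depends on the form of the effect:

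| Assumed Cingal effect | Percent users, Fisher | Mean amount, ANCOVA | Rank ANCOVA |
|---|---|---|---|
| Every subject 40% lower | 16% | 93% | 84% |
| 25% stop, the rest unchanged | 96% | 41% | 82% |
| 15% stop, the rest 20% lower | 74–78% | 66–71% | 81–82% |
| 25% stop, the rest 20% lower | 97–99% | 83–89% | 96–97% |

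Ranges in the last two rows are from separate simulation runs of the same model.

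**5. Sensitivity to the assumptions.** There were 12 settings: use on 5% or 20% of days; CV 1, 1.5 or 2; with or without extra use for another joint. The proportional effect gives 3–16% for percent users, 35–97% for mean amount and 24–93% for ranks. The stop-only effect gives 32–100%, 16–52% and 33–90%.

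**The case against.** Several arguments on the other side stand.

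- Protocol 11.3.9 repeats the wording of the neighbouring endpoints, including a baseline score that rescue use does not have, and the protocol itself lists pills between visits as exploratory and descriptive. It is therefore not certain that the protocol meant pill amount. The departure from a baseline-adjusted model with intervals remains.
- A reader might infer that the amount of rescue is lost from the report. It is not: SAP 4.1.4 still presents it by arm. Only the named secondary analysis loses sensitivity.
- A reader might infer that percent users is better only for an all-or-none effect. The two mixed rows above contradict this: it beats the mean amount in both.
- The table title might be read as use at the visit itself, which would show almost nothing because "Rescue medication will be discontinued at least 48 hours prior to Baseline and all follow-up visits". That reading is strained. The SAP section heading and the endpoint lists in both documents say through 26 weeks, so a corrected title is enough.
- The default in SAP 4.2, that "the last pretreatment observation will be used as baseline", might look like a flaw because of the washout. It applies to changes from baseline, and the Fisher analysis computes none. It matters only for the covariate in the proposed fix.
- Use for other joints might seem to count against percent users in particular. It weakens the amount analysis as well, so it does not favour the change.
- The missing intervals are not peculiar to rescue: the OMERACT-OARSI table in SAP 4.1.3.1 has the same form.

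**Conclusion.** The mismatch between protocol and SAP is plain from the text and needs no assumption. Its consequence is reduced sensitivity, not bias: if Cingal lowers use roughly in proportion without stopping it, percent users over 26 weeks would probably miss the effect (about 16% against 93% power in the main example). How large the loss is in this trial is unknown, because the documents give no usage rates, and a 40% reduction between two arms that both contain TH is itself an assumption. If cessation is a substantial part of the effect, percent users can match or beat the mean amount. The point is minor: one secondary endpoint of a pilot study, with the amount still described and with WOMAC, VAS and NRS pain unaffected.

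**What to change.** In SAP 4.1.3.9:

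- Make the main analysis mean acetaminophen pills per day from injection through week 26, with between-visit intervals as the time course.
- Name one main data source, for example the diary, with the pill count as a check.
- Use the protocol 11.3.9 model with treatment and screening-to-Baseline pills per day as covariate. Report the pairwise differences with 95% confidence intervals.
- Divide by observed days. Treat the washout alike in numerator and denominator, so that pills taken during it are not counted against excluded days. For subjects terminated early for added treatment, use days up to termination.
- Add a rank-based ANCOVA, because pill counts are skewed.
- Keep percent users through 26 weeks as supportive, with confidence intervals, and retitle the table to say through 26 weeks.

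The cost is a few lines of SAP text and one table. Pill counts, diary rescue entries and screening-to-Baseline use are already collected (protocol 9.1 and 9.3). The downside is that mean amount is less sensitive than percent users if the effect is mainly complete cessation; the rank analysis and the supportive percentage are there to cover that case.
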